Endpoints:	
Primary Endpoint:
 
• Pharmacokinetic: Plasma progesterone levels at specified time points.• Safety: Adverse events, clinical assessments (eg. vital sign, physical, etc.), clinical laboratory test.• Efficacy: Overall response rate (ORR) per protocol volumetric definition at 8 weeks. 
Secondary Endpoints:
 
• Efficacy: Progression Free survival (PFS) and Overall Survival (OS)• Exploratory: Progesterone receptor expression levels by immunohistochemistry, specified intrinsic tumor factors (genetic/epigenetic changes), levels/changes in specified serum biomarkers before and 4 weeks after treatment with progesterone, QOL assessment by the EORTC Quality of Life Questionnaire-Core 30/Brain Cancer Module-20 (EORTCQLQ30/BN20); M. D. Anderson Symptom Inventory Brain Tumor Module (MDASI-BT).
Study Population:	The patient population consists of 20-32 subjects ≥ 18 years of age with. Eligible patients must have glioblastoma at 1 st to 3 rd recurrence with KPS ≥ 60 . Recurrent GBM may be managed by surgery (no minimum enhancing disease required). Additional inclusion/exclusion criteria are specified in protocol.
Phase:	Phase I; Pilot
Description of Sites/Facilities Enrolling Participants:	Winship Cancer Institute of Emory University (Atlanta, GA).
Description of Study Intervention:	Patients will receive the following treatment: Aqueous natural progesterone for injection (25-75 mg SC) daily for up to 24 weeks.
Study Duration:	Patients will be treated for up to 24 weeks unless there is unacceptable toxicity, disease progression per protocol specification, or the patient opts to withdraw prior to that time which would result in early drug discontinuation. Patient will be followed at 4 weeks following drug discontinuation for their end of study (EOS) visit.

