15.1 Statistical consideration section: Biostatistician

This is a single arm, Phase 1 study, designed to evaluate the pharmacokinetics, safety/tolerability and efficacy of subcutaneously administer natural progesterone in subjects with recurrent glioblastoma (GBM). The study consists of two parts: Part 1) Dose finding phase; Part 2) Dose expansion phase.

Statistical design and sample size:

Dose finding phase (Part 1):

The dose finding phase will proceed using a standard 3+3 approach in order to identify the maximum tolerated dose (MTD). The study will start at Dose Level 0 with dose moving according to protocol criteria

Protocol Title: Pilot study of progesterone for recurrent GBM

(Section 5.2). For the 3+3 dose finding phase, a dose limiting toxicity (DLT) will be defined as a grade 3 or

greater toxicity that is not clearly due to the underlying disease or extraneous causes that develops in the first 28 days of starting progesterone (exceptions as noted in **Section 5.3**). Dose levels are shown on the following table:

Dose Level	Daily subcutaneous dose (mg)
-1	25
0	50
1	75

After treatment initiation of up to 6 patients at a dose level and continuation for a minimum of 4 weeks with AE assessment, enrollment to the next (higher or lower) dose level as determined by the rules will only start after data is presented to the Winship Data Safety Monitoring Committee (DSMC) and final approval is obtained for starting the next dose level. The sample size in the dose finding phase will range from 6-12.

Dose expansion phase (Part 2):

A total of 20 patients will be enrolled at the MTD (including those in the Dose finding phase at this dose level) in the dose expansion phase unless futility criteria for the expansion cohort is met. The MTD from the dose finding phase (25 mg, 50 mg, or 75 mg) administered subcutaneously 1x/day will be given in this expansion cohort until 20 patients have initiated the dose determined from the dose finding phase. The objective of the dose expansion phase is to provide a preliminary efficacy assessment, and thus no further justification for this sample size is required.

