Futility analysis - As mentioned above, there will be one interim analysis for futility. It is known that random ineffective therapies for recurrent GBM may still produce a response rate of 10%. Therefore, the overall response rate (ORR) for first 10 patients (1/2 of planned expansion cohort size) that undergo treatment with the subcutaneous progesterone at the final dose from the dose finding phase of the study will be determined. If the ORR at the 8 week assessment time point is 20% (2 of 10) or greater, then the study will be declared potentially non-futile and enrollment of the full expansion cohort (N=20) will proceed. If the ORR at this time point is 10% (1 of 10) or less, then the study will be declared futile and further enrollment will be aborted. If the study is declared futile at this interim analysis, new enrollment will be discontinued but any patients that is still on therapy at that time will be allowed to continue therapy as long as they meet criteria to continue therapy as defined in Section 8.1 (e.g. continue to not have protocol-specified progressive disease).

Analysis populations:

Safety population: All subjects enrolled in the study who received the study drug.

Efficacy population: Subjects enrolled in the study who received the study drug at the expansion dose from both the dose finding and expansion phases of study.

Data analysis plan for each objective is listed below:

Primary Objectives

Dose finding phase (Part 1):

- To determine the safety of administering daily subcutaneous natural progesterone for the treatment of patients with recurrent GBMs. The safety of this approach will be confirmed by assessing toxicity potentially attributable to the daily progesterone treatment. Toxicity will be determined by CTCAE v5.0 criteria. The MTD will be determined using the standard 3+3 approach. **Dose escalations will be reviewed by the Winship Data Safety Monitoring Committee (DSMC) (per Winship SOP 7.9 Dose Escalation Determinations for Sponsor-Investigator or Investigator Initiated Studies).** **The PI or designee will provide an update on all relevant safety data of patients entered to a dose level to the DSMC when dose escalation is planned. Upon obtaining approval from the DSMC, dose escalation can proceed.**

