- To determine the pharmacokinetics of natural progesterone given to recurrent GBM patients by subcutaneous injection. This analysis will be performed to determine what plasma drug levels can be achieved in recurrent GBM patients with subcutaneous administration of natural progesterone and whether this is in line with what was previously determined in healthy subjects.

Dose expansion phase (Part 2):

- To determine the overall response rate (ORR) of eligible patients with recurrent GBM treated with daily subcutaneous natural progesterone. This primary analysis will be performed on all patients treated at the expansion dose (from either the dose finding or expansion phases). In particular, we will be looking for the fraction of patients that are able to maintain at least stable disease (SD), given our expectation that, for patients showing a contrast enhancing recurrence, all will continue to progress unless they are receiving an effective therapy. ORR will be reported, and an exact 95% confidence interval will be reported using the Clopper-Pearson method. There will be one interim analysis for futility that is described above that may halt enrollment before full accrual of the expansion cohort.

Secondary Objectives

Dose expansion phase (Part 2):

- To determine and compare the progression free survival of eligible patients with recurrent GBM. Patients on this study will be followed for progression free survival (PFS), which is defined from the time of pre-treatment MRI to the time of either radiographic progression or death, whichever occurs first. Both actuarial PFS curves and 24-week PFS (for expansion dose patients and all patients as separate analyses) will be estimated using the Kaplan-Meier method, and compared to matched historical controls using log-rank tests and univariate Cox proportional hazards models. The matched effects will be estimated by a Cox model with a robust variance estimator. A 95% confidence interval will be provided for 24-week PFS using the Greenwood formula to estimate the standard error.

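### The matched PFS and OS hazard ratios rest on a robust-variance Cox model with about 20 matched sets and no small-sample reference, so a default 95% interval would cover about 92–94%

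*Combined protocol and SAP*

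**What the plan says.** In Section 15.1, under Secondary Objectives, PFS and OS are each to be "compared to matched historical controls using log-rank tests and univariate Cox proportional hazards models". The next sentence deals with the matching: "The matched effects will be estimated by a Cox model with a robust variance estimator". It appears in the same words for both endpoints.

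The number of treated patients is given in three places:

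- **Expansion dose.** Section 15.1 states: "A total of 20 patients will be enrolled at the MTD". This count includes dose-finding patients treated at that dose. One interim look stops enrollment if at most 1 of the first 10 patients has stable disease or better at 8 weeks.
- **Two analysis sets.** The survival comparisons are run "for expansion dose patients and all patients as separate analyses".
- **Overall total.** The synopsis (1.1) states: "The patient population consists of 20-32 subjects". The accrual table in Section 9 gives a maximum of 26.

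The only confidence level stated for these endpoints belongs to the Kaplan-Meier estimate: "A 95% confidence interval will be provided for 24-week PFS using the Greenwood formula to estimate the standard error", with a matching sentence for OS. No level, sidedness or test threshold is given for the hazard ratio. Also absent are the number of controls per patient, the clustering unit, and whether a normal or a t reference is used.

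**The concern.** The robust (sandwich) variance is a large-sample tool. When it is clustered to respect matching, its accuracy depends on the number of independent sets. If each treated patient anchors one set, adding controls does not add sets. With about 20, the estimate tends to fall below the true variance and is itself noisy. Multiplying its square root by 1.96 makes the interval too short for both reasons.

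This is the only listed method that addresses the matching, and comparison with matched historical controls is a stated secondary objective for both PFS and OS. For its primary efficacy endpoint the same section specifies an exact Clopper-Pearson interval, so the plan already uses a small-sample method elsewhere. If nothing more is specified, the hazard-ratio intervals will follow the software default and be labelled 95% while covering somewhat less.

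**Working it through.** The plan gives no power, event count, effect size or error rate for these comparisons, so there is no figure to reproduce. The check is a simulation under no effect.

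**Inputs from the documents**

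- Expansion-dose analysis: 20 treated patients, hence about 20 sets; about 10 after a futility stop (15.1).
- All-patients analysis: the rules in 5.2 visit at most two dose levels, with up to 6 patients at one and 20 at the other, so 6 + 20 = 26 sets. The synopsis maximum would give 32.

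**Assumptions, because the documents are silent**

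- One treated patient plus 1–3 controls per set.
- Gamma frailty shared within a set, variance 0 or 0.5.
- Censoring of 0, 15 or 30%.
- Variance clustered on the matched set.
- Two-sided 5% level with a normal reference.

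**Formulas.** For G sets, V = A⁻¹(Σ U_g²)A⁻¹. Here A is the Cox information for the single treatment covariate and U_g is the sum of score residuals in set g. The test rejects if |β̂|/√V > c, and the interval is exp(β̂ ± c√V). The default is c = 1.96; the alternative is the 97.5% point of t on G − 1 degrees of freedom. The estimator agreed with a standard package on a test data set (β̂ = −0.5952, robust SE 0.4648 in both).

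**Results.** The main grid used 20,000 replicates per setting (Monte Carlo SE about 0.2 points). The wider grid used 6,000, with up to 5 controls per patient and frailty variance up to 1 (Monte Carlo SE 0.3–0.4 points).

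| Sets | Rejection, c = 1.96, main grid | Same, wider grid | Rejection, t on G − 1, main grid | Mean robust SE ÷ true SD, main grid | t width ÷ 1.96 width |
|---|---|---|---|---|---|
| 10 | 7.4–9.8% | 6.8–10.2% | 4.1–6.1% | 0.86–0.93 | 1.15 |
| 20 | 6.1–7.8% | 5.6–8.1% | 4.6–6.1% | 0.93–0.96 | 1.07 |
| 26 | 5.8–7.0% | 5.5–7.6% | 4.6–5.8% | 0.94–0.97 | 1.05 |
| 32 | not run | 5.1–6.9% | not run | not run | 1.04 |

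A separate run of 4,000 replicates per setting gave 5.7–7.8% at 20 sets, 5.8–7.4% at 26 and 8.0–10.3% at 10. Its SE ratio at 20 sets was 0.92–0.95, that is, 5–8% too small; the main grid gives 4–7%. Its t-based rejection was 4.5–6.0% at 20 sets and 4.6–6.5% at 10.

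**Plausibility check at 20 sets.** If the SE were too small by a fixed factor r, the rejection rate would be 2[1 − Φ(1.96r)]. With r = 0.96 this is 2[1 − Φ(1.882)] = 6.0%. With r = 0.92 it is 2[1 − Φ(1.803)] = 7.1%. The simulated rates lie in this region. They can exceed it because the SE also varies between trials.

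**Coverage.** 100% − 6% = 94% and 100% − 8% = 92% at 20 sets.

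**Ties.** Progression is read at scheduled MRIs, so event times will be tied. Rounding times up to an 8-week grid (median of 4 months assumed, 3,000 replicates) still gave 6.2–8.2% at 20 sets.

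**The case against.** **The text is silent, not wrong.** Section 15.1 does not say 1.96, does not state a 95% interval for the hazard ratio and does not define the cluster. This stands, and the figures are conditional on those choices. The direction depends on them too. In a check at 10 sets, a robust variance not clustered on the set rejected 7.1–7.9% without frailty but only 3.1–4.0% with it, which is conservative. Clustering on the set is the natural reading of a robust variance for matched effects, but it is an inference.

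**A reader might infer that the planned analysis rejects 7–10% of the time.** It does not. That range belongs to about 10 sets. At 20 sets the main grid gives 6.1–7.8%, and 6.1–6.8% with 15–30% censoring.

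**A reader might also infer that a futility stop makes a false claim of benefit more likely, or that evidence is overstated equally in both directions.** The documents do not support this. About 10 sets arise only when at most 1 of 10 patients has stable disease or better at 8 weeks, which selects on early progression and hence on PFS itself. A simulation with equal true hazards and 8-week progression-free rates of 10–30% gave, conditional on a stop, rejection favouring progesterone in 0.03–2.6% of trials. Rejection in the harm direction was 6.6–33%. Selection dominates there and a t reference does not remove it. Ten is also a floor, since no accrual pause is stated while the 8-week results mature.

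**It hardly matters.** This largely stands. The endpoints are secondary, the expansion is described as a preliminary assessment, and no decision turns on a 7% wider interval. The undefined matching ratio, matching variables and control source are larger gaps.

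**Conclusion.** The point holds as a minor one. In the expansion-dose analysis at full accrual, with about 20 matched sets, the robust standard error is about 5–8% too small (4–7% in the largest run). A nominal 5% test rejects about 6–8% under no effect, and a 95% hazard-ratio interval covers about 92–94%. In the all-patients analysis the rejection rate is about 6–7% at 26 sets, and 5.1–6.9% if the stated maximum of 32 were reached.

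These figures assume clustering on the matched set, a normal reference, a two-sided 5% level and 1–3 controls per patient (up to 5 for the figure at 32 sets). The within-set correlation and censoring are also assumed. At about 10 sets the unconditional rate is about 7–10%, but it should not be quoted as the error rate after a futility stop, for the reason given above. Nothing here bears on the response-rate analysis or its interval.

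**What to change.** In Section 15.1, for both PFS and OS, add that the matched Cox interval and test use the robust variance clustered on the matched set, with a t reference on (number of matched sets − 1) degrees of freedom. State the matching ratio in the same place, so that the number of controls per set is fixed in advance.

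The cost is a sentence or two for each endpoint and a small change to the analysis code; no new data are needed. Intervals widen by 2.093/1.96 = 1.07, or 7%, at 20 sets, and by 5% at 26. The correction is approximate: rejection was 4.6–6.1% at 20 sets in the main grid, so it is slightly conservative in some settings and slightly liberal in others. It does not correct the selection that follows a futility stop.

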- Patients who received any other in anti-tumor agents (including investigational anti tumor agents, but excluding avastin) must be off therapy for 4 weeks prior to initiating progesterone on study. Patients on avastin at enrollment will be allowed to be maintained on their current dose of avastin when they begin progesterone. Patients receiving anti-coagulation therapy are excluded.
- Patients that underwent resection for their recurrent GBM need to wait at least 4 weeks before they can initiate progesterone treatment.
- Patients with active or recent (within 6 months) thromboembolic disease are excluded.
- Patients with current ongoing therapy with estrogen/progesterone (including hormonal contraceptives) are excluded. Would need to stop this form of birth control at least 7 days prior to initiation of therapy to be eligible.

10. Local Number of Participants

We will be recruiting all participants (up to 32 patients) at the Winship Cancer Institute of Emory University. Patients will be registered after signing of the informed consent document and meeting all entry requirements.

11. Recruitment Methods

Subjects will be recruited from recurrent GBM patients referred by neurosurgery, neuro-oncology or radiation oncology. Initial screening will be conducted/reviewed by clinical investigators and/or their trained designee (e.g. research nurse, research coordinator, etc.). Cases will be identified from the neurosurgery/neuro-oncology/radiation oncology outpatient clinics or neurosurgery/oncology inpatient services. After potential subjects have been identified, their clinical care team at Winship will inform potential subjects about the known benefits and potential risks of a clinical trial as well as other available treatment options.

Protocol Title: Pilot study of progesterone for recurrent GBM

Some of the subjects recruited for this protocol will be patients being treated at Emory and under the care of one or more of the study investigators. Some potential subjects will be identified by their treating physician and referred to Emory for possible participation in the protocol.

No incentives are provided to patients for trial participation.

Study personnel will notify Winship Central Subject Registration (WCSR) by email at [contact], once subject has been consented for a trial.

Email notification must be done within 24 hours after consent has been obtained and it will include scanned copies of:

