- To determine and compare the overall survival of eligible patients with recurrent GBM. Patients on this study will be followed for overall survival (OS) which is defined from the time of pre-treatment MRI to the time of death. Both actuarial OS curves and 24-week OS (for expansion dose patients and all patients as separate analyses) will be estimated using the Kaplan-Meier method, and compared to matched historical controls using log-rank tests and univariate Cox proportional hazards models. The matched effects will be estimated by a Cox model with a robust variance estimator. A 95% confidence interval will be provided for 24-week OS using the Greenwood formula to estimate the standard error.

Exploratory Objectives:

Dose expansion phase (Part 2):

- To determine whether progesterone receptor levels within the tumor correlates with response to daily subcutaneous natural progesterone. This will be examined for both expansion dose patient and all patients as separate analyses. Original tumor and any recurrent tumor samples will be assessed for progesterone receptor expression levels by immunohistochemistry and these results will be correlated with response assessment to determine whether there is any correlation. Progesterone receptor staining by IHC will be scored on a scale of 0-4 by standard criteria and then compared with response assessment using standard statistical tests such as two sample t-tests or Mann-Whitney U tests, where appropriate, to determine whether there is any correlation between expression level and response.
- To determine if other intrinsic tumor factors (mutations and genomic loss/gains, see **Section 5.7** for specific details) correlates with response to daily subcutaneous natural progesterone. This will be examined for both expansion dose patient and all patients as separate analyses. Each of the tumor mutational and genomic loss/gain factors will be scored and these results will be correlated with response assessment using chi-square tests or Fisher's exact tests, where appropriate.

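### The Greenwood-based 95% interval for 24-week PFS has no stated scale and no rule for a curve at zero; at n = 20 and a true rate of about 10% or lower it does not reach 95% coverage

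*Combined protocol and SAP*

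**What the plan says.** Under Secondary Objectives in Section 15.1, 24-week PFS is estimated by Kaplan-Meier "for expansion dose patients and all patients as separate analyses", and "A 95% confidence interval will be provided for 24-week PFS using the Greenwood formula to estimate the standard error". A parallel sentence covers survival: "A 95% confidence interval will be provided for 24-week OS using the Greenwood formula to estimate the standard error". Neither sentence says whether the interval is formed on the plain, log or log-log scale, or what is reported if the curve has reached zero.

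The expansion-dose set is 20 patients, including dose-finding patients treated at that dose (Section 15.1). The all-patients set is at most 32 (Section 10). For ORR, another proportion in the same expansion-dose patients, Section 15.1 says "an exact 95% confidence interval will be reported using the Clopper-Pearson method".

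The documents give no expected 24-week PFS rate. The nearest figure is in the futility paragraph of Section 15.1: "It is known that random ineffective therapies for recurrent GBM may still produce a response rate of 10" percent. Section 2 defines ORR as stable disease or better at 8 weeks. Section 15.1 also expects that every patient with a contrast-enhancing recurrence will progress unless the therapy works.

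**The concern.** The Greenwood standard error is a large-sample quantity. With 20 patients and few of them progression-free, the estimate lies near zero, where a symmetric interval is too short and can have a negative lower limit. If nobody is progression-free, the estimated standard error is zero.

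That outcome is foreseeable. Where ineffective therapy leaves about 10% of patients with stable disease or better at 8 weeks, the share still progression-free at 24 weeks should be about that or lower. The result would then be reported as 0% with a 95% interval of 0 to 0%, or with no interval at all, although 0 of 20 is compatible with true rates up to about 17%. Since 24-week PFS is a named secondary result to be set beside historical controls, readers would take its interval at face value.

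**Working it through.** **Inputs.** n = 20 for the expansion dose (Section 15.1) and up to 32 for all patients (Section 10). Confidence level 95%; two-sided, z = 1.96 (assumed, as sides are not stated). True 24-week PFS rate p: not stated, so 5% to 25% is examined. Censoring before 24 weeks: no rate stated, so none is used for the exact results and 10% for a sensitivity check. The plan gives no PFS precision or power figure; the only stated figure to test is the nominal 95%.

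**Reduction.** Without censoring before 24 weeks, S = x/n for x progression-free patients, and Greenwood's variance reduces to S(1 − S)/n.
- Plain: S ± 1.96 × √[S(1 − S)/n].
- Log-log: S raised to the power exp(±1.96 × s), with s = √[(1 − S)/(nS)] / |ln S|. It is undefined at S = 0 and is counted there as not covering.
- Clopper-Pearson: exact binomial limits; for x = 0 the upper limit is 1 − 0.025^(1/n).

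Coverage is the sum of Binomial(n, p) probabilities over every x whose interval contains p.

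**Example, plain scale, n = 20.**
- p = 5%: only x = 1 to 4 cover. P(0) = 0.95^20 = 35.8% and P(x > 4) = 0.3%, leaving 63.9%.
- p = 10%: x = 1 to 6 cover. P(0) = 0.90^20 = 12.2% and P(x > 6) = 0.2%, leaving 87.6%.
- p = 15%: x = 2 to 7 cover. 1/20 now also misses, because its upper limit is 0.05 + 1.96 × √(0.05 × 0.95/20) = 14.6%. Coverage is 81.9%.

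**Coverage at n = 20, no censoring.**

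| True rate | Plain | Log-log | Clopper-Pearson | P(0/20) |
|---|---|---|---|---|
| 5% | 63.9% | 62.6% | 98.4% | 35.8% |
| 10% | 87.6% | 86.7% | 98.9% | 12.2% |
| 15% | 81.9% | 93.9% | 97.8% | 3.9% |
| 20% | 92.1% | 97.9% | 97.9% | 1.2% |
| 25% | 89.5% | 96.2% | 96.2% | 0.3% |

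**Source of the loss.** Given at least one progression-free patient, plain coverage is 63.9/(100 − 35.8) = 99.6% at a true 5% and 87.6/(100 − 12.2) = 99.7% at 10%. Log-log is 97.5% and 98.7%. At 10% or below the defect is therefore almost entirely the zero outcome. At 15% the plain-scale shortfall is a separate fault, since 1/20 misses too.

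**Individual results.**
- 0/20: plain 0 to 0%; log-log undefined; exact 0 to 16.8%, from 1 − 0.025^(1/20).
- 2/20: plain −3.2% to 23.2%; log-log 1.7% to 27.2%; exact 1.2% to 31.7%.

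**Sensitivity to censoring.** In simulated Kaplan-Meier data (8,000 runs, n = 20, 10% censored), plain coverage is about 61%, 86%, 87% and 91% at true rates of 5, 10, 15 and 20%. The picture does not change.

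**All-patients set, n = 32.** Plain: 80.2%, 84.0%, 86.3%, 89.0% and 91.4% at 5, 10, 15, 20 and 25%. Log-log: 78.6% at 5%, 95.4% at 10%, and 94.8 to 95.9% from 15 to 25%. For 0/32 the exact upper limit is 10.9%.

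**Futility stop.** Enrolment ends if at most 1 of the first 10 has stable disease or better at 8 weeks. At the plan's 10% rate this has probability 0.9^10 + 10 × 0.1 × 0.9^9 = 34.9% + 38.7% = 74%. With about 10 patients, plain coverage is 65% at a true 10% and 40% at 5%; log-log is 64% and 39%. These are not conditioned on having stopped. For 0/10 the exact upper limit is 1 − 0.025^(1/10) = 31%.

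**The case against.** **The plan does not say the interval is plain.** It uses Greenwood for the standard error only. Negative limits and the 82% coverage at a true 15% belong to the plain scale; log-log uses the same standard error and does well from about 15% up at n = 20. This stands. A reader might infer that any Greenwood-based interval fails across the whole 5 to 25% range, and the calculations do not support that. What remains is an unstated scale and, on every scale, no rule for zero.

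**Undercoverage and collapse to a point are largely one defect at low rates.** This also stands, as the conditional figures show. On the log-log scale, moreover, software would return no interval at 0/20, so false precision arises only on the plain scale.

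**The low rate is an assumption.** The 10% is an 8-week figure for ineffective therapy. Patients with resected disease need no minimum enhancing tumour (Section 9), and patients on avastin may stay on it (Section 5.5); either could raise PFS. The expectation of universal progression concerns enhancing recurrences only. Full enrolment of 20 also requires at least 2 of 10 with stable disease or better at the interim, which makes 0/20 less likely. Against that, a stop leaves a smaller n and a worse interval.

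**OS.** A reader might infer that the parallel OS sentence is equally faulty. At assumed 24-week survival of 40, 50, 60 and 70%, plain coverage at n = 20 is 92.8 to 95.9% and log-log 92.8 to 97.3%. Only extreme survival would matter: a true 90% mirrors 10% and gives 88% on the plain scale.

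**Consequence.** Futility is judged on ORR, and the historical comparison uses log-rank tests and Cox models. Nothing is decided on this interval.

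**Conclusion.** The point holds in limited form. Followed as written, Section 15.1 yields a 24-week PFS interval that falls short of its stated 95% at n = 20 if the true rate is about 10% or lower: 88% or 87% (plain or log-log) at 10%, and 64% or 63% at 5%. The main cause is that 0/20 has no usable interval. From 15 to 25% the fault is confined to the plain scale. A futility stop at about 10 patients makes matters worse.

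This rests on an assumed low rate, suggested but not stated by the documents, and on little censoring before 24 weeks. Coverage in small samples moves up and down between neighbouring true rates, so single percentages indicate size only. The harm is to the reporting of a secondary result in a pilot, not to any trial decision. No material error is shown for 24-week OS at mid-range survival. The change is worth making because the weak case is foreseeable and the remedy is already in the plan for ORR.

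**What to change.** In the PFS paragraph of Section 15.1, keep Kaplan-Meier for the curve and replace the Greenwood sentence with a rule for the 24-week interval:
- If 24-week status is known for all patients, report the exact 95% Clopper-Pearson interval, as for ORR.
- If some patients are censored before 24 weeks and 0 < S < 1, use Clopper-Pearson limits with effective sample size S(1 − S)/Var(S), where Var(S) is Greenwood's variance.
- If S is 0 or 1, that effective sample size is 0/0. Use exact limits with the number of patients whose 24-week status is known, counting those who progressed or died earlier.

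The same rule may be used for 24-week OS for consistency, although no need for it is shown there.

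The cost is a few lines of SAP text, no added data, and somewhat wider, slightly conservative intervals (coverage 96 to 99% at n = 20 for true rates of 5 to 25%). Coverage of the censored version was not computed and should be checked by a short simulation before it is adopted. Wilson limits are a less conservative alternative: at n = 20 they cover 92.5%, 95.7%, 97.8% and 95.6% at true rates of 5, 10, 15 and 20%, and give 0 to 16.1% for 0/20.
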